4.1.4 End of the Study

The study is complete once the last patient visit has taken place.

4.2 Standard Operating Procedure for Sample Collection and Preparation

4.2.1 Digital and Manual Planimetry

4.2.1.2 Digital Planimetry

1. Digital camera to take photograph of wound with calibration scale adjacent to wound
2. Computer based calculation of wound size

4.2.1.3 Manual Planimetry

1. Transparent, flexible planimetry grid placed onto wound. Edge of wound traced with permanent marker pen.
2. Calculate area of ulcer and log into clinical data sheet.

4.2.1.1 Urine

1. Mid stream urine sample
2. Transfer to 50ml Falcon tube
3. Aliquot 10 x 1ml samples into 2ml Eppendorf
4. Transported to South Kensington Campus on dry ice
5. Freeze at -80 degrees Celsius for storage

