4.1 Procedures and Assessments

4.1.1 Initial Assessment

- A full history and examination will be completed.
- Venous severity scoring (4).
- CEAP (Clinical-etiologic-anatomy-pathophysiology) scoring (5).
- Colour venous duplex to establish integrity of the venous system.
- Ankle brachial pressure index.
- Routine blood tests: Full blood count, urea, electrolytes, glucose, glycosylated haemoglobin (if patient suffers from diabetes).
- Assessment of wound healing: This will be performed using digital planimetry by which electronic representations of the ulcer are formed and the area calculated.
- Wound ulcer fluid – Two techniques performed simultaneously.
 1. “Occlusive dressing technique” (6). This technique involves the placement of a clear adherent dressing over the ulcer. After ninety minutes in a seated position. The dressing is pierced with a 21 gauge needle and any accumulated fluid is sampled.
 2. “Filter disc technique” (7). This involves placement of filter discs on top of the ulcer bed separated by a permeable transparent dressing to filter out solid material.
- Urine sampling: A mid-stream urinary sample shall be requested from the patient in a standard specimen pot without additives.
- Special blood tests: A sample shall be taken from the antecubital fossa and placed in a standard bottle without additives.
- The patient's ulcer will be managed using compression bandaging.

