4.2.1.2 Blood

1. Sampled from antecubital fossa avoiding the use of alcohol based skin preparation. Collection into plain blood bottles. 21g needle and syringe technique
2. Transfer into 15ml Conical Dome Polypropylene Falcon Tube
3. Stand for 30 minutes to clot on dry ice
4. Centrifugation at 2,500g for 10 minutes to obtain serum from supernatant fluid
5. Transfer serum into 10ml Falcon tube
6. Aliquot 0.4ml into 1.5ml Eppendorf x 2 (minimum, ideally 3)
7. Freeze at -80 degrees Celsius for storage

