4.2.1.3 Leg Ulcer Fluid

a. Occlusive Dressing Technique (6)

1. Ulcerated area covered in Tegaderm dressing
2. 90 minutes with the leg dependent in a seated position
3. Fluid aspirated with hypodermic 21g needle and syringe
4. Fluid transferred into 10ml 15ml Conical Dome Top Polypropylene Falcon tube and kept on dry ice
5. Collected fluid kept on ice and centrifuged within 30 minutes at 13,000g
6. Supernatant filtered using methylcellulose filter (8)
7. Transfer 0.4ml into 1.5ml Eppendorfs
8. Transport to South Kensington Campus on dry ice
9. Flash frozen and stored at -80 degrees Celsius

b. Filter Disc Technique (7)

1. Preprepared 1cm² absorptive filters from Whatman 54 paper, sterilised in ethanol and oven dried at 60 degrees Celsius. Preweighed in sterile 2ml tubes.

2. Sterile Tegapore mesh placed cut into 4cm² segments and placed onto ulcer. Ten discs placed on top of mesh.
3. After 90 minutes, disc removed from mesh and placed back into tube.
4. Transferred to South Kensington Campus on dry ice
5. Putative Imperial method – Analyse filter discs directly after separation into aqueous and organic extracts
6. Aqueous extract – mass spectrometry and NMR
7. Organic extract – Mass spec ± examination for eicosanoids / inflammatory molecules

Tarloton method

1. Filter discs reweighed to determine quantity of fluid absorbed and placed into extraction buffer.
2. Four hours of agitated extraction and fluid removed for freezing and stored at -80 degrees.

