4.3 Proposed Analyses

These assays would be performed on ulcer fluid, urine and blood samples collected at the initial and each subsequent assessment.

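### Urine is aliquoted and frozen with no spin or filter, so any cells or bacteria present may release their contents into samples assayed for neutrophil proteins and metabolites

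*Combined protocol and SAP*

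**What the plan says.** Section 4.1.1 describes collection: "A mid-stream urinary sample shall be requested from the patient in a standard specimen pot without additives". Section 4.2.1.1 then gives five steps: the mid-stream sample, transfer to a 50 ml tube, "Aliquot 10 x 1ml samples into 2ml Eppendorf", "Transported to South Kensington Campus on dry ice", and "Freeze at -80 degrees Celsius for storage". Neither sections 4.1.2 and 4.4.2 nor the visit summary in 4.6 adds a processing step for urine.

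Two other specimens are separated before storage. Section 4.2.1.2 (Blood) has "Centrifugation at 2,500g for 10 minutes to obtain serum from supernatant fluid". Section 4.2.1.3, part a (occlusive dressing fluid) has "Collected fluid kept on ice and centrifuged within 30 minutes at 13,000g", and the supernatant is then filtered.

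The assays are not limited to ulcer fluid. Section 4.3 states: "These assays would be performed on ulcer fluid, urine and blood samples collected at the initial and each subsequent assessment". The lists include S100A9 and lactotransferrin as first-line assays (4.3.3), MMP9 and lipocalin 2 as second-line assays that depend on sample volume (4.3.4), and NMR and mass spectrometry profiling (4.3.1).

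The only infection exclusion in section 3 concerns the studied leg. No dipstick, urinary cell count or culture is described.

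**The concern.** Whole urine can contain leucocytes and bacteria. It is general laboratory knowledge, not something the documents state, that freezing and thawing can rupture them. S100A9, lactotransferrin, MMP9 and lipocalin 2 are abundant in neutrophils, and untargeted profiling also picks up bacterial products. A patient with white cells or bacteria in the bladder could therefore show a raised inflammatory marker in urine that says nothing about the ulcer. Correcting for urine dilution would not remove it.

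At stake is the use of urine, one of three specimen types, for the first objective in section 1.1, predicting from biological markers who will not heal. Urine is taken at seven visits (weeks 0, 1, 2, 4, 8, 12 and 20) and at five more (weeks 21, 22, 23, 25 and 28) if the ulcer is unhealed. A handling gap in the written procedure would run through the whole urine bank. With no urine screen recorded, affected samples could not be recognised afterwards.

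**Working it through.** **Steps that remove cells or particles before freezing, as written**

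| Specimen | Spin | Filter or mesh |
|---|---|---|
| Urine (4.2.1.1) | none | none |
| Blood (4.2.1.2) | 2,500g, 10 minutes | none |
| Ulcer fluid, occlusive (4.2.1.3 a) | 13,000g | filter |
| Ulcer fluid, filter disc (4.1.1; 4.2.1.3 b) | none | permeable dressing that holds back solids |

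Urine is the only specimen with neither. In the urine sequence the aliquots go onto dry ice at step 4, so freezing has in effect begun before the -80°C step. A separation step has to come before step 3.

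**Is the contrast clean?** Not entirely. Blood is left to clot on dry ice before its spin. Occlusive fluid is put on dry ice in one step and kept on ice in the next, also before its spin. Read literally, those specimens might also freeze before separation.

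**Illustrative size.** The plan has no figure to reproduce, and every input here is an assumption: one marker on the log scale with SD 0.7; a true difference of 1 SD (0.7); 24 v 16 of the 40 patients; a two-sided t-test at 5%; and a fraction p of samples in both groups reading f times too high.

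Contamination raises the variance from 0.7² = 0.49 to 0.49 + p(1 − p)(ln f)². The difference in SD units becomes 0.7 divided by the square root of that.

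- f = 10, p = 0.05: 0.49 + 0.0475 × 5.302 = 0.742; SD 0.861; difference 0.81 SD
- f = 10, p = 0.10: 0.49 + 0.09 × 5.302 = 0.967; SD 0.983; difference 0.71 SD
- f = 10, p = 0.20: 0.49 + 0.16 × 5.302 = 1.338; SD 1.157; difference 0.61 SD
- f = 2, p = 0.20: 0.49 + 0.16 × 0.480 = 0.567; SD 0.753; difference 0.93 SD

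Simulated power (40,000 t-tests per setting; 86% with no contamination):

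| Elevation | 5% affected | 10% affected | 20% affected |
|---|---|---|---|
| 2-fold | 84% | 82% | 80% |
| 5-fold | 77% | 71% | 60% |
| 10-fold | 69% | 58% | 45% |

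A rank test starts at 84% and at tenfold gives 75%, 65% and 51%. It softens the loss but does not remove it.

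**False positives.** With no true difference and equal contamination in both groups, the t-test rejects in about 5% of runs in every setting. With 5% affected in the group of 24 and 20% in the group of 16, tenfold, it rejects in 19%. With those two rates swapped, it rejects in 14%.

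**The case against.** The strongest reply is that nothing shows the effect to be large, or even present in a given sample. The documents give no urinary leucocyte counts or rate of bacteriuria. The sample is mid-stream, a method meant to limit contamination. The affected fractions and fold elevations above have no source in the plan, and at twofold the loss of power is small. Section 4.5 promises only univariate analysis of the assays, so the t-test is an assumption too. All of this stands: the effect is possible, and its size cannot be known from the documents.

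A second reply is that a spin removes intact cells only. Proteins already released in the bladder and bacterial metabolites already in solution stay in the supernatant. This also stands, so the power table describes contaminated urine as a whole and not what one centrifuge step would recover.

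Third, urine is secondary. The aims centre on the ulcer, section 4.3.4 ties the comprehensive metabolic profile to ulcer fluid, and MMP9 and lipocalin 2 may not be run at all. The healing analysis and the ulcer-fluid results are untouched. That limits the consequence to exploratory urine markers, but section 4.3 does plan those markers at every assessment.

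A reader might also infer that urine alone is exposed while all ulcer fluid is spun. The text does not support that: filter-disc fluid has no listed spin, and the dry-ice wording for blood and occlusive fluid leaves their own order of freezing and separation unclear. This weakens the contrast but does not supply the step missing from the urine procedure.

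**Conclusion.** The point holds as a gap in specimen handling. Followed exactly, section 4.2.1.1 banks urine with its cells and bacteria in it, and this cannot be reversed once the aliquots are frozen. The likely consequence is added noise in exploratory urine markers, in proportion to cell and bacterial content that the documents do not report.

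Two stronger readings should be resisted. One is that the urine results will be contaminated; the documents support only that they may be. The other is that this would create false differences between patients who heal and those who do not. Under equal contamination the false-positive rate stays near 5%. It rises only if contamination differs by healing status, and nothing in the documents shows that it would.

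The power figures (86% falling to 84–80% at twofold and 69–45% at tenfold, for 5% to 20% of samples affected) rest wholly on the assumptions listed and should be read as illustration. The case for acting rests on the irreversibility and the low cost.

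**What to change.** Between steps 2 and 3 of section 4.2.1.1, add a line: centrifuge the urine, for example at the 2,500g for 10 minutes already used for blood, and aliquot only the supernatant. The spin must be done before the aliquots go onto dry ice. The occlusive-fluid procedure already lists its spin before transport, so no new type of equipment is needed. The cost is ten minutes per sample and loss of the cell pellet.

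Optionally, because the spin leaves dissolved material behind, dip residual urine for leucocytes and nitrite, record the result, and repeat the urine analyses without positive samples. The cost is a dipstick per visit and a few flagged samples.

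Separately, the dry-ice and ice wording before the spins in sections 4.2.1.2 (Blood) and 4.2.1.3 (Leg Ulcer Fluid) should be reconciled, so that the order of freezing and separation is clear for every specimen.

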4.2.1.2 Blood

1. Sampled from antecubital fossa avoiding the use of alcohol based skin preparation. Collection into plain blood bottles. 21g needle and syringe technique
2. Transfer into 15ml Conical Dome Polypropylene Falcon Tube
3. Stand for 30 minutes to clot on dry ice
4. Centrifugation at 2,500g for 10 minutes to obtain serum from supernatant fluid
5. Transfer serum into 10ml Falcon tube
6. Aliquot 0.4ml into 1.5ml Eppendorf x 2 (minimum, ideally 3)
7. Freeze at -80 degrees Celsius for storage

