4.4.2 Sample Labelling and Storage

Samples will be marked with the patient's unique identifying number and a suffix to the sample will be added as per the specimen type.

Blood serum	B
Urine	U
Wound fluid – Occlusive dressing	fX
Wound fluid – Filter disc	fN
Filter disc for analysis	fW

Prior to analysis, all samples will be stored in a secure freezer at the Section of Computational and Systems Medicine, South Kensington Campus Imperial College London at -80 degrees Centigrade.

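### The blood procedure has whole blood clot on dry ice before the spin that is meant to yield liquid serum; the wound-fluid procedure gives two holding conditions before one spin

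*Combined protocol and SAP*

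**What the plan says.** In section 4.2.1.2 Blood, blood is drawn into plain bottles and moved to a Falcon tube (steps 1 and 2). Step 3 reads "Stand for 30 minutes to clot on dry ice". Step 4 reads "Centrifugation at 2,500g for 10 minutes to obtain serum from supernatant fluid". The serum is then transferred and aliquoted (steps 5 and 6), and freezing at -80 degrees comes last, at step 7.

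In section 4.2.1.3 Leg Ulcer Fluid, occlusive dressing technique, step 4 puts the aspirated fluid in a "Conical Dome Top Polypropylene Falcon tube and kept on dry ice". Step 5 reads "Collected fluid kept on ice and centrifuged within 30 minutes at 13,000g". Step 6 filters the supernatant.

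Elsewhere in section 4.2 dry ice appears only as a transport medium: "Transported to South Kensington Campus on dry ice" (urine, step 4), "Transport to South Kensington Campus on dry ice" (occlusive fluid, step 8) and "Transferred to South Kensington Campus on dry ice" (filter disc, step 4). Section 4.4.2 adds: "Prior to analysis, all samples will be stored in a secure freezer at the Section of Computational and Systems Medicine, South Kensington Campus". It lists the blood specimen as serum.

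**The concern.** Serum is obtained by letting blood without additive clot and then spinning off the liquid. Step 3 names that purpose but places the tube on a freezing medium for half an hour. If whole blood freezes before it is separated, its cells may lyse and release their contents into what is later stored as serum. Nothing done to the stored aliquot afterwards can reverse that.

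Section 4.3 sends blood for assay at the initial and every subsequent assessment, and the objectives in section 1.1 are to predict non-healing from biological markers and to follow those markers over time. Recruitment is at two trusts, in London and Cambridge. If staff at one follow the step literally and staff at the other read it as a slip, their serum would not be comparable, and a handling difference could pass for a biological one.

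For the occlusive wound fluid the problem is smaller: step 5 can be carried out as written, but step 4 asks for something different for the same specimen.

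**Working it through.** The plan states no figure on this point. The check is a reading of the steps in order, plus a count of the collections they govern.

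**Blood, steps in order (4.2.1.2 Blood)**

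| Step | Instruction in brief | State it requires or produces |
|---|---|---|
| 1–2 | Plain bottle, then Falcon tube | Liquid whole blood, not separated |
| 3 | 30 minutes to clot, on dry ice | Clotting is the purpose; the medium freezes |
| 4 | 2,500g for 10 minutes | Needs liquid serum above a clot |
| 5–6 | Transfer and aliquot serum | Liquid |
| 7 | Freeze at -80 degrees | First planned freezing |

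Section 4.1.1 confirms that the bottle has no additive, so clotting has to come before the spin. There is no thaw between steps 3 and 4, and no other section amends step 3. The only premise from outside the documents is physical: dry ice, at about -78 degrees Celsius, is cold enough to freeze blood. How fast or how fully it would do so is not estimated, because the documents give no blood volume or contact conditions.

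**All dry-ice instructions in section 4.2**

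| Route | Step | Use | Before a spin? |
|---|---|---|---|
| Urine | 4 | Transport | No |
| Blood | 3 | Holding | Yes |
| Occlusive fluid | 4 | Holding | Yes |
| Occlusive fluid | 8 | Transport | No, after spin and filtration |
| Filter disc | 4 | Transport | No |

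The total is 5: 3 for transport and 2 for holding before a spin. The two holding instructions are the ones questioned here.

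A transport step to South Kensington appears in 3 of the 4 specimen routes and is absent only for blood, although section 4.4.2 stores all samples there. The phrase in step 3 may therefore be a displaced transport line, or it may be dry ice written for ice. The documents do not settle which.

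**Occlusive fluid.** Steps 4 and 5 name dry ice and then ice for one specimen ahead of one spin. Read as a sequence, they would need a transfer and possibly a thaw, and neither is described.

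**Collections governed by blood step 3**

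- Patients: 40 (sections 2 and 4).
- Sampling visits to week 20: weeks 0, 1, 2, 4, 8, 12, 20 = 7 (sections 4.1.1 and 4.1.2).
- Further visits if unhealed at week 20: weeks 21, 22, 23, 25, 28 = 5 (section 4.1.3).
- Week 0 only: 40 × 1 = 40.
- Through week 20: 40 × 7 = 280.
- With u patients unhealed at week 20: 280 + 5u. At u = 0 this is 280; at u = 40 it is 280 + 200 = 480 (40 × 12).

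These counts assume full recruitment and attendance. They would be lower with missed visits, or if patients who heal early stop being sampled.

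**The case against.** The strongest reply is that this is a visible slip that experienced staff would not act on. Step 3 says what it is for, step 4 plainly needs liquid, and freezing is scheduled only at step 7. The document also seems to use the term loosely: urine travels on dry ice and is only then frozen, and occlusive fluid travels on dry ice and is only then flash frozen. Other unedited text nearby, such as two tube sizes given together in occlusive step 4, points the same way. The harm depends on literal compliance, no section shows that the two sites process blood differently, and the collection counts say nothing about bias or lost data.

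Much of that is fair as a limit on consequences. A slip is plausible, the counts are upper bounds, and divergence between sites is a possibility, not a finding. Scope is limited too. Section 4.3.4 places the comprehensive metabolic profile in ulcer fluid, section 4.3.2 uses wound exudate for the angiogenesis assays, and urine, filter-disc fluid, ulcer area and healing are untouched. The wound-fluid conflict is minor, since step 5 is workable and comes later.

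None of it removes the conflict in the blood procedure. The transport uses of dry ice come after processing or with no spin to follow, so they do not make freezing before a serum spin harmless. The two likely slips also call for different corrections, so staff who spot the error still cannot tell from the text what was meant.

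**Conclusion.** The concern holds and should be corrected before the procedure is used. As written, blood step 3 conflicts with its own purpose and with step 4, and nothing in the document repairs it. This is certain as to the wording. The consequence is conditional: with literal compliance, it touches every scheduled blood collection, from 40 at baseline to a maximum of 480, and any damage to the serum could not be undone. No effect on assay values, bias or variance can be quantified from the documents. The occlusive-fluid discrepancy between steps 4 and 5 is real but secondary. The absent blood-transport line is a gap in detail; it carries no weight in this conclusion beyond showing that the intended meaning of step 3 is open.

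**What to change.** In section 4.2.1.2 Blood, replace the dry-ice wording in step 3 with a single clotting condition specified by the laboratory, one that keeps the blood unfrozen until the step 4 spin and is identical at both sites. At the same time, state how blood or serum reaches South Kensington, with any dry ice confined to after serum separation.

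In section 4.2.1.3 Leg Ulcer Fluid, reconcile occlusive steps 4 and 5 to one laboratory-specified holding condition that leaves the fluid liquid for the spin and filtration.

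If any blood has already been collected under this text, record how step 3 was actually carried out at each site, so that affected serum can be identified before analysis.

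The cost is two wording corrections and one added line on transport, with no extra patients, visits, samples or procedures.

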4.2.1.3 Leg Ulcer Fluid

a. Occlusive Dressing Technique (6)

1. Ulcerated area covered in Tegaderm dressing
2. 90 minutes with the leg dependent in a seated position
3. Fluid aspirated with hypodermic 21g needle and syringe
4. Fluid transferred into 10ml 15ml Conical Dome Top Polypropylene Falcon tube and kept on dry ice
5. Collected fluid kept on ice and centrifuged within 30 minutes at 13,000g
6. Supernatant filtered using methylcellulose filter (8)
7. Transfer 0.4ml into 1.5ml Eppendorfs
8. Transport to South Kensington Campus on dry ice
9. Flash frozen and stored at -80 degrees Celsius

b. Filter Disc Technique (7)

1. Preprepared 1cm² absorptive filters from Whatman 54 paper, sterilised in ethanol and oven dried at 60 degrees Celsius. Preweighed in sterile 2ml tubes.

2. Sterile Tegapore mesh placed cut into 4cm² segments and placed onto ulcer. Ten discs placed on top of mesh.
3. After 90 minutes, disc removed from mesh and placed back into tube.
4. Transferred to South Kensington Campus on dry ice
5. Putative Imperial method – Analyse filter discs directly after separation into aqueous and organic extracts
6. Aqueous extract – mass spectrometry and NMR
7. Organic extract – Mass spec ± examination for eicosanoids / inflammatory molecules

Tarloton method

1. Filter discs reweighed to determine quantity of fluid absorbed and placed into extraction buffer.
2. Four hours of agitated extraction and fluid removed for freezing and stored at -80 degrees.

4.3 Proposed Analyses

These assays would be performed on ulcer fluid, urine and blood samples collected at the initial and each subsequent assessment.

4.3.1 Metabonomics

This technique has been pioneered at Imperial College London and is defined as a technique to broadly measure the “global metabolic metabolic response of living biological systems to biological stimuli or genetic manipulation.”(9)

We would seek to obtain a comprehensive metabolic profile of a chronic venous ulcer throughout its cycle of healing or failure to heal. This would be performed using established techniques of nuclear magnetic resonance spectroscopy and mass spectrometry.

Biomarkers of potential significance will be identified from the comprehensive list of metabolites using chemometric and bioinformatics software.

